#### Surveys

Participants will complete the third weekly "long-term" surveys (Table 2, third column).

#### **Blood pressure**

Repeat visit 2 procedures.

# VISITS 5-7 (Days 29, 36, 43)

#### **Monitor Symptoms**

Same as visit 1. For complaints that are musculoskeletal issues that can be temporarily avoided by the EP [name] recommending GlucoseZone videos that avoid the injured area, then such videos can be continued without PCP clearance.

#### Surveys

Participants will complete the fourth - sixth weekly "long-term" surveys (Table 2, third column).

#### **Interviews**

Participants will complete weekly audiotaped 30min semi-structured interviews about the app (Appendix 10).

August 13, 2024

Version #7

#### **Blood pressure**

Repeat visit 2 procedures.

#### **VISIT 8 (Day 50)**

#### **Monitor Symptoms**

Same as visit 1.

#### Surveys

Participants will complete the seventh weekly "long-term" survey (Table 2, third column).

#### Interviews

Participants will complete the same interview as Visits 5-7.

# **Quantitative Satisfaction Survey (Appendix 11)**

The above weekly semi-structured interviews will be supplemented by a quantitative survey at the end of the 4 weeks. It will include the system usability scale (10 Likert-style items assessing aspects such as ease of use and degree of technical support needed,  $\alpha$ =.91) for each of the above tools and each biosensor, Likert-style survey items specially designed for each of the novel mobile tools based upon the above questions, net promoter score, and implementation outcome measures (acceptability, appropriateness, feasibility;  $\alpha$ =.85-.91). We will evaluate participant use metrics to determine intervention component feasibility (i.e., diary and biosensor adherence, use of videos, receipt of text messages).

#### **Start Ecological Momentary Assessments**

Ecological momentary assessments are repeated sampling of behaviors and experiences in real-time, which serves to a) minimize recall bias and b) capture the effect of real-world surroundings.

Participants will download Ilumivu or Qualtrics software. They will start momentary surveys 5x daily (Table 2, second column) and continue through the end of Visit 10. For each participant we will establish five windows programmed to cover their self-expected wake window. For example, a participant who normally wakes up at 7am and goes to bed at 10pm would have windows of 7-10am, 10am-1pm, 1pm-4pm, 4pm-7pm, 7pm-10pm. Ilumivu or Qualtrics will push one survey at a random time within each window. The survey remains accessible for 40min then expires if not completed. Participants will be instructed not to answer surveys while driving.

#### **Blood pressure**

Repeat visit 2 procedures.

#### Put Actigraph GT9X (i.e., blinded hip and wrist watch) back on

Repeat visit 2 procedures.

#### **VISIT 9 (Day 57)**

#### **Monitor Symptoms**

Same as visit 1.

#### Survevs

Participants will complete the eighth weekly "long-term" survey (Table 2, third column).

#### **Blood pressure**

Repeat visit 2 procedures.

August 13, 2024

Version #7

#### **VISIT 10 (Day 64)**

#### **Monitor Symptoms**

Same as visit 1.

#### **Surveys**

Participants will complete the nineth weekly "long-term" survey (Table 2, third column).

#### Interview

Interview on Motivation States (Appendix 12). The interview will be conducted by personnel from Case Western Reserve University over HIPAA-compliant Zoom. All other procedures are conducted by personnel from Yale University.

#### **Blood pressure**

Repeat visit 2 procedures.

#### **PAYMENT FOR PARTICIPATION**

#### From consent form:

First, you will be paid for each weekly visit. These payments start at \$5, increase by \$3 for each week in a row that you complete, and returning to \$5 if you miss a week. Second, you will be paid \$1 for each day you wear the CGM, each day you wear the Fitbit, each day you complete the daily survey, each day you wear the blinded watch on your hip, and each night you wear it on your wrist. Third, you will be paid \$100 if you complete 50%-79% of the 5x daily surveys, and \$200 if you complete 80%-100% of them. This third payment is released once you mail back the study supplies using a prepaid label. Therefore, the total possible compensation is \$577.

You may be responsible for paying state, federal, or other taxes for the payments you receive for being in this study. Taxes are not withheld from your payments.

Please note payments are only provided for completion of research assessments, not the exercise. So we do not consider them to impact exercise outcomes.

# STUDY PROTOCOL

# **Social Behavioral Template**

#### 6.2 Method of Assignment/Randomization (if applicable)

Not applicable (not a randomized study)

# 6.3 Adverse Events Definition and Reporting

Every event that is reported to either the principal investigator or the designated research associates by the subject or medical staff caring for the subject and which meets the criteria will be documented.

An adverse event report will be generated for each event. The report will include

- \*description of the event
- \*likelihood of being related to the study
- \*when and how it was reported
- \*any official chart records or documentation to corroborate the event

The report will be supplied to the principal investigator, the study physicians Drs. [name] and [name], the data and safety monitoring board (DSMB), the Yale University IRB, and the NIDDK program official responsible for the award [name] [name]. The DSMB is chaired by [name] (statistician at Yale Center for Analytical Sciences) who currently chairs a DSMB for the National Institute of Aging and has served on 10+ DSMB boards. The other members are [name] (board-certified endocrinologist at University of Virginia) and [name], MS (exercise physiologist at Yale-New Haven Hospital Heart and Vascular Center). No DSMB members are affiliated with the study or investigators.

#### Timeline for reporting

Events that may require a temporary or permanent interruption of study activities by the Principal Investigator or sponsor to avoid potential harm to subjects will be verbally reported immediately (if possible) with a written report filed within 5 calendar days.

Reportable Events (which are events that are serious or life-threatening and unanticipated (or anticipated but occurring with a greater frequency than expected) and possibly, probably, or definitely related to study procedures) will be filed as a written report within 5 calendar days.

Unanticipated Problems Involving Risks to Subjects or Others (UPIRSOs) will be filed as a written report within 5 calendar days. UPIRSOs applicable to this study include:

- Adverse device effects from any of the biosensors (continuous glucose monitor, smartwatch, insulin smartpen, hip accelerometer) beyond the ones expected (sect 2.2, last 2 bolded sections).
- Adverse events or injuries that are serious, unexpected, and related;
- Breaches of confidentiality involving risks;
- Interim analyses altering the risk/benefit profile by identification of increased risks;
- Revisions to safety information, such as MedWatch Reports, that meet the definition of a UPIRSO:
- New information indicating an unexpected increase in risks or decrease in potential benefits (e.g., literature/scientific reports or other published findings);
- Protocol deviations, violations, or other accidental or unintentional changes to the protocol or procedures involving risks or with the potential to recur;

August 13, 2024

Version #7

- Unapproved changes made to the research to eliminate an apparent immediate hazard to a subject;
- Other problem or finding (e.g., loss of study data or forms) that an investigator or research staff member believes could influence the safe conduct of the research.

Events that do not require prompt reporting and are only documented at regular reports (twice yearly to DSMB, annual renewals to the Yale IRB, and annual progress reports to NIDDK) are:

- Anticipated adverse events (described in section 2.2)
- Adverse device effects that are non-serious, anticipated, or unrelated;
- Adverse events or injuries that are non-serious, expected, or unrelated;
- Deaths not attributed to the research (e.g., from "natural causes," accidents, or underlying disease when the Principal Investigator and the DSMB have ruled out any connection between the study procedures and the subject's death);
- Interim analyses not altering the risk/benefit profile;
- Protocol deviations or violations unlikely to recur or not involving risks to subjects;
- · Subject complaints that were resolved or complaints not involving risks
- Problems or findings not involving risk (unless the PI believes the information could affect subjects' willingness to continue in the research)

Any action resulting in a temporary or permanent suspension of this study (e.g., IRB actions, or actions by the investigators) will be immediately reported to the appropriate NIDDK program official.

# 6.4 Reaction Management

This protocol is listed in section 2.2 risks and pasted here for reference.

**Study questionnaires and interviews:** Participants may experience some distress when discussing factors important to diabetes, diabetes management, and psychosocial stressors.

The probability of such responses is uncommon and the typical magnitude of responses is mild. No such instances were reported in our previous pilot studies.

Research participants who report negative psychological reactions to the research protocol, or negative emotional reactions to diabetes elicited during participation in the research study, will be referred to their regular clinical provider. If research staff determine that the degree of psychological reaction is severe, the physician staff of the study ([name] or [name]) will be contacted to assess the participant and determine whether acute urgent referral is needed.

#### 6.5 Withdrawal Procedures

#### APPROVED BY THE YALE UNIVERSITY IRB 8/14/2024

Protocol Number 2000035846

August 13, 2024

Version #7

- Participants may withdraw at any time without penalty by telling study staff or writing to the PI ([name], Yale School of Medicine, Section of General Internal Medicine, [name])
- Upon withdrawal, no further information will be collected.
- Researchers may still use information collected prior to withdrawal.
- Participants withdrawing will be asked to return all supplies using the packing tape and prepaid label included in the box (see section 6.1.1 visit 1, "mailing")
- Participants withdrawing may request copies of their Fitbit and blood glucose data up to the point of withdrawal
- Researchers may withdraw participants from the study if they have not followed instructions, suffer injury or illness making further exercise unsafe, meet individual stopping criteria (>1 episode of severe hypoglycemia, 1 episode of diabetic ketoacidosis not closely related to pump site failure, or blood pressure >160/100mmHg), or the researchers otherwise believe it is not in their best interest to continue.

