Severe hypoglycemia will be defined as any blood glucose level resulting in symptoms which require outside intervention to control (including but not limited to confusion and loss of coordination). Severe hyperglycemia will be defined as blood glucose >500mg/dL, presence of urine ketones or other signs and symptoms of diabetic ketoacidosis (including but not limited to weakness and fatigue, confusion, shortness of breath). Patients will be asked to contact emergency services should these events occur. Specifically, Yale-affiliated patients with T1D have access to a 24-hour hotline with access to nurse and/or physician advice or can choose to call 911. Non-Yale-affiliated patients will be asked to call 911 or contact their providers' after-hours staff (all patients will submit provider information to the study team at study start). The study team will be notified of the event within 24 hours via daily diaries; moreover all participants will have the PI's direct contact information should they choose to contact him earlier by phone or email. Our team will then notify the patient's primary diabetes provider (if not already notified) and all study-related exercise will be suspended until patient receives further advice from their diabetes provider regarding next steps which may include modified exercise routines or suspension of the study altogether. All serious adverse events such as severe hypoglycemia and hyperglycemia will be reported to the PI verbally within 24 hours of study staff being notified and to university's IRB committee in writing within 5 business days. In the case of >1 episode of severe hypoglycemia or 1 episode of diabetic ketoacidosis not closely related to pump site failure, the participant will be removed from the study and referred to their diabetes care provider for follow-up.

**Exercise-related injuries:** Exercise may cause muscle soreness/pain, muscle strain, cardiovascular events, and tiredness during or after the activity.

The probability and magnitude of such injuries varies based upon factors such as the individual participant's fitness level and the difficulty of the exercise routines. Our previous pilot studies (sect. 1.2) had no injuries or muscle strains. The American Heart Association Scientific Statement notes that the frequency of exercise-related out-of-hospital cardiac arrest among the general population ages 35-90yr was measured at 3.0 per 100,000 person-years.

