### 4.2 Outcome Variables/Endpoints

### 4.2.1 Primary Outcome Variables/Endpoints

### **PRIMARY AIMS**

Primary Objective 1. Evaluate the intervention for feasibility

**Outcome Variable 1-1-1.** Participant use metrics (i.e., % completion of diary, % wear-time of biosensors, frequency of video usage, % received of text messages).

**Primary Objective 2.** Evaluate the intervention for acceptability (i.e., user satisfaction)

**Outcome Variable 1-2-1.** System usability scale (10 Likert-style items assessing aspects such as ease of use and degree of technical support needed,  $\alpha$ =.91) augmented with Likert-style survey items specially designed for this intervention.

**Primary Objective 3.** Evaluate the mathematical robustness of the intervention by evaluating its predictive performance upon exercise behavior.

**Outcome Variable 1-3-1.** Prediction accuracy for exercise adherence (receiver-operator characteristic, precision-recall).

**Outcome Variable 1-3-2.** Frequency of expected patterns in blood glucose safety hazards around exercise.

Outcome Variable 1-3-3. Changes in blood glucose resulting from exercise.

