For the 2-week familiarization period until visit 4, the trainer will review InPen data after days 1, 3, 7, 10, and 14 days to check if data are being transmitted consistently with reasonable values. The trainer will also talk with the participant at each visit and query of there are any issues or concerns. Trainer will follow up with participant to troubleshoot as needed. We will start with a bank of standard troubleshooting techniques from our procedure manual, then involve Medtronic customer service or a senior clinician from the research team as needed.

Participants will set up the Actigraph GT9X hip accelerometer (i.e., blinded hip and wrist watch) on their own belt, elastic waistband, or a belt we provide. They are asked to wear the device on the hip for all waking hours except bathing, and on the dominant wrist (i.e., opposite wrist of the Fitbit) for sleep. The device samples data at 30Hz and aggregates it into 60-second epochs. Non-wear periods are defined by Troiano's algorithm^94 confirmed against participant logs of non-wear periods; previously our wear time exceeded literature standards (14.1±1.9 waking hours per day for 5.4±1.0 out of 7 days). Participants will receive a daily morning SMS survey through Ilumivu or Qualtrics asking them to log that morning's attachment time and previous night's removal time.

Participants will measure blood pressure by standard home monitoring procedures. We will take the average of 2 brachial artery measurements after ≥12 hours abstention from acute blood pressure confounders (exercise, caffeine, alcohol, tobacco, nicotine) and ≥5 minutes of quiet rest using the Omron BP760N, which includes a rigid cuff that minimizes fitting errors. If the measurements differ by >5 mmHg, then a third will be taken and the closest two will be averaged. In the event of a result meeting the home BP monitoring criteria for uncontrolled accelerated hypertension (systolic >160 mmHg and/or diastolic >100 mmHg), the participant will be withheld from exercise participation until BP can be reassessed at least one day later. In the event of a second occasion meeting these values, the participant will be removed from the study and referred to their healthcare provider for follow-up.

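### The quantitative acceptability survey is given only at Visit 8 and section 6.5 ends data collection at withdrawal, so participants who start the app and stop for good before then have no survey score

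*Combined protocol and SAP*

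**What the plan says.** Section 6.5 sets out withdrawal in one list. After saying that participants may leave at any time, it states "Upon withdrawal, no further information will be collected" and then "Researchers may still use information collected prior to withdrawal". Four items after the first of these, the list turns to staff decisions: "Researchers may withdraw participants from the study if they have not followed instructions, suffer injury or illness making further exercise unsafe", or if they meet an individual stopping criterion. Sections 2.2 and 6.1.1 (Visit 2) use similar language for those criteria. For repeated severe hypoglycemia or ketoacidosis, "the participant will be removed from the study and referred to their diabetes care provider for follow-up". For a second high blood pressure result, "the participant will be removed from the study and referred to their healthcare provider for follow-up". None of these places provides a survey at exit.

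Section 4.2.1 names one outcome variable for acceptability, 1-2-1: the system usability scale, "augmented with Likert-style survey items specially designed for this intervention". Table 1 schedules the exit survey at Visit 8 (Day 50) only, and the Visit 8 text agrees: "The above weekly semi-structured interviews will be supplemented by a quantitative survey at the end of the 4 weeks".

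The interviews on the app take place at Visits 5, 6, 7 and 8. The synopsis lists interview themes as an acceptability outcome, and section 7.2 analyzes the weekly interviews under Hypothesis 1-2. The same section summarizes the survey descriptively. It gives no denominator and no rule for participants who did not reach Visit 8.

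**The concern.** Some reasons for leaving early may be connected with how the app performed for that person: injury, a glycemic event, not following instructions, or dislike of the program. If those people are systematically without a score, the survey describes the participants for whom the intervention went well enough to continue. Hypothesis 1-2 asks both for positive feedback and for suggested refinements, and early stoppers are an obvious source of the second.

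The missing-data section (7.7) does not help. It screens missingness against predictors and earlier values with a view to the final models. A survey given once has no earlier value of its own, and section 7.2 plans no model for it. A score not collected when the person stops cannot be recovered later.

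**Working it through.** **Inputs.** Enrollment of 24, retention of 88% and 21 expected completers (section 7.1). App start at Visit 4, Day 22; first app interview at Visit 5, Day 29; survey at Visit 8, Day 50; last visit at Visit 10, Day 64 (Table 1). Pilot overall rating of 3.4, SD 0.9, out of 5 (section 1.2.1). The pilot rating is only a stand-in for the mean that this study will observe.

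**The plan's own figure.** 24 × 0.88 = 21.12, which gives the stated 21 completers. The remainder is 24 − 21 = 3, or 3/24 = 12.5%.

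**Why 3 is an upper estimate.** The 88% refers to participants who completed; read as completion of the whole study, it runs to Day 64. Losses between Day 50 and Day 64 come after the survey. Losses before Day 22 come before any use of the app, so there is no score to recover. Only losses between Visit 4 and Visit 8 count.

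**What each early stopper contributes to acceptability.**

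| Last visit completed | Survey score | App interviews kept |
|---|---|---|
| Visit 4 | none | 0 |
| Visit 5 | none | 1 |
| Visit 6 | none | 2 |
| Visit 7 | none | 3 |
| Visit 8 or later | yes | 4 |

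**Bounds on the mean.** With k scores missing and an observed mean of 3.4 on a 1-to-5 scale, the mean over all 24 lies between ((24 − k) × 3.4 + k × 1)/24 and ((24 − k) × 3.4 + k × 5)/24.

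- k = 1: (78.2 + 1)/24 = 3.30 to (78.2 + 5)/24 = 3.47
- k = 2: (74.8 + 2)/24 = 3.20 to (74.8 + 10)/24 = 3.53
- k = 3: (71.4 + 3)/24 = 3.10 to (71.4 + 15)/24 = 3.60
- k = 6, if retention is worse than planned: (61.2 + 6)/24 = 2.80 to (61.2 + 30)/24 = 3.80

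**One-sided illustration.** If all 3 leavers would have scored 2.0, the mean over 24 is (71.4 + 6)/24 = 3.2. If all would have scored 1.0, it is 3.1. The survey mean would then be 0.2 to 0.3 points too high. These leaver scores are assumptions. For scale, the standard error of the mean at n = 21 with the pilot SD is 0.9/√21 = 0.20.

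**The case against.** The strongest reply is that acceptability does not rest on the survey. Section 4 says that the primary objectives are addressed by observation of feasibility and by the weekly satisfaction interviews. The survey supplements those interviews, and section 7.1 sizes the study first for their saturation. They begin one week after the app starts, and earlier data are kept. This stands. A reader might infer that acceptability as a whole is measured only in those who last the 4 weeks; the documents do not support that. The gap concerns the survey scores, plus all acceptability data from anyone who leaves between Visits 4 and 5.

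A reader might also infer that every safety event leads to removal. That is not so. Sections 2.2 and 8.7 provide for suspending exercise and lifting the suspension. A single severe hypoglycemia episode does not trigger removal, mild hypoglycemia is not exclusionary, and section 6.5 says that staff may withdraw participants, not that they must. The four prior trials cited in section 2.2 had no severe hypoglycemia or ketoacidosis. So it would be wrong to say that the study loses its participants with hypoglycemia. Nor does the course of safety events go unrecorded: sections 6.3 and 8.7 require a report for each adverse event and tracking of dropout reasons. Neither supplies a survey score.

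The words on ending data collection directly follow the item on participants' own withdrawal. Applying them to staff removal is therefore an inference, though a fair one, because the list uses the same verb for both and makes no exception. Finally, Hypothesis 1-2 has no numerical threshold and the analysis is descriptive, so no stated decision turns on 0.2 or 0.3 of a point. That limits the weight of the point but does not remove it.

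**Conclusion.** The point holds for the quantitative outcome 1-2-1. Participants who start the app and stop permanently before Visit 8 have no survey score, and the plan states neither a denominator nor a way of handling them. The expected number is at most about 3 of 24. With 3 missing and an observed mean of 3.4, the mean over all 24 could be 3.1 to 3.6. This rests on the planned 88% retention, on the pilot rating as a stand-in, and on reading section 6.5 to include removal by staff.

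A reader might conclude that the survey mean is biased upward. That is plausible from the listed reasons for removal, but the documents do not show what leavers would have answered, and the bounds run in both directions. This is a modest, inexpensive improvement to a primary outcome of a descriptive pilot, not a flaw that undermines it.

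**What to change.** - In section 6.5, distinguish stopping the app or exercise, by choice or by staff, from withdrawing consent to data collection. Keep the rule against further collection for withdrawal of consent only, and state which of the two applies to removal by staff.
- For those who stop but still consent, offer the existing Appendix 11 exit survey and the app interview once, at the stopping contact. Participants may decline.
- In section 7.2, report survey results for all who started the app. State the number who started and the number who answered, and show early stoppers separately.
- Leave all clinical suspension, stopping and removal rules unchanged. Continuing sensors or momentary surveys after removal is not needed to close this gap.

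The cost is a small change to the protocol and consent wording and at most about three early surveys and interviews. The drawback is that early scores rest on less than 4 weeks of use, which is why they should be shown separately.
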